6.0 Statistical analysis

6.1 Sample size

Phase 1: Approximately 220000 OPCRDR patients with active asthma will be available for inclusion in this phase. Of these, approximately 85000 have moderate to severe asthma (GINA steps 4 & 5).

Phase 2: Approximately 220000 OPCRDR patients and 440000 CPRDR patients with active asthma will be available for inclusion in this phase (85000 moderate to severe from OPCRDR and 170000 moderate to severe from CPRDR). Approximately 260000 of the CPRDR patients will have linked secondary care data (HES): the HES records are required to identify secondary care service use and costs, and for some measures of disease severity.

6.2 Software used

Stata MP/6 version 15.1.

6.3 CONSORT chart

A CONSORT-type chart, describing the number and proportion of patients retained and excluded at each step of the inclusion/exclusion criteria will be generated for each study phase.

6.4 Demographic and clinical characteristics of patients at index date (phase 1 and 2)

Phase 1: The demographic and clinical characteristics at index date of patients included in the analysis will be tabulated: this will include the number and proportion of patients with each of the comorbidities of interest. For completeness, the number of patients with no comorbidities will also be reported. As it will not be possible to distinguish between inactive and active comorbidity and mild to moderate/severe comorbidity for all comorbidities of interest without linked HES data, this will be reported as the number of patients with active/inactive comorbidity.

Phase 2: A similar set of outputs will be produced for the second phase. In addition, the number and proportion of patients whose comorbidity is inactive, active, mild and

moderate/severe will be tabulated for each comorbidity using the primary care and linked HES data.

Patient characteristics at index date will be reported for the study population using the following conventions:

- Continuous variables will be summarised using descriptive statistics: n (non-missing sample size), percentage of non-missing, mean, standard deviation, median, inter-quartile range (25th and 75th percentile), maximum and minimum.
- For categorical measures, the frequency and percentages (based on the non-missing sample size) of observed levels will be reported.

Comorbidity prevalence will be estimated for each comorbidity cluster by dividing the number of patients in the cluster by the total number of patients eligible for inclusion in the study.

The ratio of observed to expected cases for each comorbidity cluster will be estimated by dividing the observed prevalence of the cluster by the expected prevalence of the cluster (the product of the prevalence of each individual disease in the cluster).

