2.2 Study objectives

Phase 1: The primary objective is to estimate the frequency of each combination/cluster of T2 type comorbidities in a real world active asthma population, and to select, by consensus, a limited set of common comorbidity clusters for further investigation.

Phase 2: The primary objective is to describe the overlap between these clusters and between individual comorbidities within the clusters in terms of patient demography, and asthma severity, resource utilisation and costs.

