6.5 Identification and selection of comorbidity clusters (phase 1)

There are over 500 possible combinations of the 9 comorbidities of interest. The prevalence of each combination of comorbidities will be tabulated (including patients with no comorbidities) (see mock table in appendix 8). Clusters will be ranked by prevalence. The ratio of observed cases to expected for each cluster and cumulative proportion of population accounted for at each step will be calculated.

Visualisations of the frequency and age distribution of comorbidity in the asthma population will be produced. A table with the source data will accompany each figure. The first figure will chart the frequency of comorbidities in the study population (see illustrative example in appendix 9). The second figure will chart the mean number of comorbidities in the asthma population by age group and gender (appendix 10).

A small set of key comorbidity clusters will then be selected by consensus for further analysis in phase 2. This will be based on their clinical importance, prevalence, observed/expected ratio and cumulative proportion of population included.

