13.8 Appendix 8: Mock comorbidity prevalence table

comorbidity									rank	prevalence	obs/exp ratio	number of patients	cum. percentage of pop.
1	2	3	4	5	6	7	8	9					
•									1	20.0%	-	2000	20%
									⋮				
•	•	•				•		•	33	3.5%	1.5	350	54%
									⋮				
	•	•			•		•		154	0.5%	7.3	50	95%
									⋮				
•	•		•	•	•	•		•	270	0.0%	1.0	1	100%

Adapted from: van den Bussche H , Koller D , Kolonko T , et al . Which chronic diseases and disease combinations are specific to multimorbidity in the elderly? Results of a claims data based cross-sectional study in Germany. BMC Public Health 2011;11:101

13.9 Appendix 9: Mock example of figure illustrating the frequency of comorbidity in the asthma population

[figure not shown]

Figure 1
 Frequency (in %) of the number of chronic conditions within the list of 46 conditions in the non-multimorbid sample (light grey columns) and the multimorbid sample (dark grey columns) and mean and median for both samples.

Source: van den Bussche H , Koller D , Kolonko T , et al . Which chronic diseases and disease combinations are specific to multimorbidity in the elderly? Results of a claims data based cross-sectional study in Germany. BMC Public Health 2011;11:101

13.10 Appendix 10: Mock example of figure illustrating the mean number of comorbidities in the asthma population by age group and gender

[figure not shown]

Figure 2
 Mean number of chronic conditions according to age and gender in the non-multimorbid and the multimorbid sample. Means were calculated for each year of life until 80. Due to the small number of cases in old age, we generated four age groups for age > 80 years before calculation.

Source: van den Bussche H , Koller D , Kolonko T , et al . Which chronic diseases and disease combinations are specific to multimorbidity in the elderly? Results of a claims data based cross-sectional study in Germany. BMC Public Health 2011;11:101

13.11 Appendix 11: Mock example of figure illustrating the association between the individual diseases in the selected clusters

[figure not shown]

Figure 1
Disease associations in multimorbidity clusters based on triads with a prevalence $\geq 1\%$ and an observed/expected ratio ≥ 2 in the female population with ≥ 3 chronic conditions.

Source: Schäfer I, Kaduszkiewicz H, Wagner HO, et al. Reducing complexity: a visualisation of multimorbidity by combining disease clusters and triads. BMC Public Health 2014;14:1285.

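### The observed/expected ratio takes its expected value from an inclusive definition of a cluster, while the Phase 1 table needs exact combinations; the protocol never says which a cluster is

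*Protocol*

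**What the plan says.** Section 6.4 gives both parts of the ratio. The observed prevalence comes from "dividing the number of patients in the cluster by the total number of patients eligible for inclusion in the study". The divisor is "the expected prevalence of the cluster (the product of the prevalence of each individual disease in the cluster"). No factor enters for the diseases a patient does not have, and membership of a cluster is not defined as having exactly, or at least, the listed diseases.

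Section 6.5 describes the table that carries the ratio. It starts from the statement "There are over 500 possible combinations of the 9 comorbidities of interest". It continues: "The prevalence of each combination of comorbidities will be tabulated (including patients with no comorbidities"). The ranking is by prevalence, and then: "The ratio of observed cases to expected for each cluster and cumulative proportion of population accounted for at each step will be calculated". The mock table in Appendix 8 has a column headed "cum. percentage of pop", which runs to 100%.

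Section 6.5 then names four considerations for the consensus choice of Phase 2 clusters: clinical importance, prevalence, the observed/expected ratio, and the share of the population covered. Section 2.2 sets the Phase 2 objective to "describe the overlap between these clusters and between individual comorbidities within the clusters".

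**The concern.** The two halves of the ratio appear to count different things. A product of marginal prevalences is the independence expectation for patients who have the listed diseases, whatever else they have. The Section 6.5 table is built as a partition. If clusters were inclusive, the row with no comorbidities would contain everybody, and adding prevalences down the table would count patients more than once.

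An observed/expected ratio is read against 1, and ratios are compared across clusters. If the value under independence differs from cluster to cluster, neither reading is safe. Diseases that truly occur together can score below 1, and a cluster lacking a common disease is marked down for that reason alone. Because the ratio is a named input to the Phase 2 selection, the distortion could influence which clusters are studied further. With about 220000 patients in Phase 1 this would be systematic bias, which sample size does not remove.

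**Working it through.** **Number of combinations.** Nine diseases, each present or absent, give 2^9 = 512 patterns including none, or 511 without it. This reproduces the protocol's figure of over 500. The count itself fits either definition; it is the no-comorbidity row and the cumulative share that call for exclusive patterns.

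**Value of the ratio under independence.** Let p be the prevalence of each disease and C the set in the cluster.

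- Exact combination: observed = Π p (in C) × Π (1 − p) (not in C). Dividing by the protocol's expected value, Π p (in C), leaves Π (1 − p) over the absent diseases.
- At least these diseases: observed = Π p (in C), so the ratio is 1.

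On exact combinations the ratio is therefore below 1 for 511 of the 512 patterns; only the all-nine pattern gives 1.

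**A bound from the protocol's own figure.** Section 1.0 puts allergic rhinitis at 25% to 100% of asthma patients. At 25%, any exact cluster without it has a ratio under independence of at most 1 − 0.25 = 0.75, and the bound falls as that prevalence rises.

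**Example pairs.** The protocol gives no single-disease prevalence in asthma for the other eight conditions, so these are assumptions: atopic dermatitis 20%, urticaria 10%, allergic conjunctivitis 10%, chronic rhinosinusitis 5%, nasal polyps 3%, food allergy 2%, anaphylaxis 1%, eosinophilic oesophagitis 0.1%, with allergic rhinitis at 25%.

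- Atopic dermatitis + allergic rhinitis: 0.95 × 0.97 × 0.90 × 0.90 × 0.98 × 0.999 × 0.99 = 0.72
- Chronic rhinosinusitis + nasal polyps: 0.75 × 0.80 × 0.90 × 0.90 × 0.98 × 0.999 × 0.99 = 0.47
- Food allergy + anaphylaxis: 0.75 × 0.80 × 0.90 × 0.90 × 0.95 × 0.97 × 0.999 = 0.45

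Each should be 1.00. With allergic rhinitis at 60%, 0.75 is replaced by 0.40 and the last two become 0.25 and 0.24.

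**Range over other assumptions.** Prevalences (%) are in the order atopic dermatitis, allergic rhinitis, chronic rhinosinusitis, nasal polyps, urticaria, allergic conjunctivitis, food allergy, eosinophilic oesophagitis, anaphylaxis.

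| Set | Assumed prevalences | Ratio under independence, all pairs | Largest ÷ smallest |
|---|---|---|---|
| Low | 10, 15, 2, 2, 5, 5, 1, 0.1, 1 | 0.66–0.85 | 1.3 |
| Mid | 25, 30, 5, 4, 12, 15, 3, 0.1, 3 | 0.35–0.64 | 1.8 |
| High | 40, 60, 15, 10, 20, 30, 8, 0.5, 5 | 0.09–0.37 | 3.9 |

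The low set puts allergic rhinitis below the protocol's 25%, so it is lenient to the plan.

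**Can the order reverse?** In the mid set, suppose rhinosinusitis and polyps occur together 1.5 times as often as chance, with the other seven diseases independent of the pair. The plan's ratio is 1.5 × 0.369 = 0.55. Atopic dermatitis + allergic rhinitis with no excess scores 0.64. The pair with true clustering reads as avoidance and falls below the pair with none.

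**Do matched terms repair it?** In one simulation of 220000 independent patients (mid set), atopic dermatitis + allergic rhinitis gave 0.64 by the plan's formula on exact combinations, 1.00 with the (1 − p) factors added, and 1.00 with at-least counts over the plain product. For the rarer rhinosinusitis + polyps pair the three values were 0.43, 1.16 and 1.02. The expected exact count there is only 220000 × 0.05 × 0.04 × 0.369 ≈ 162, so a relative standard error near 1/√162 ≈ 8% makes 1.16 about two standard errors from 1.

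**Mock table.** The figures in Appendix 8 fit neither definition. For exact combinations, a first row of 20% and rank 33 at 3.5% need a cumulative share of at least 20 + 32 × 3.5 = 132%; the table shows 54%. For inclusive clusters, no disease could exceed the 20% first row, so a five-disease cluster at 3.5% needs a ratio of at least 0.035 / 0.20^5 ≈ 109; the table shows 1.5. They are placeholders and settle nothing.

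**The case against.** The strongest reply is that the protocol nowhere calls clusters mutually exclusive. If belonging to a cluster means having at least its diseases, the product is the right expectation and there is no bias. Several places suit that meaning: the overlap objective in Section 2.2, the disease-pair list in Section 6.6, the model figure in Appendix 11 (triads among patients with three or more conditions), and the dash shown as the ratio for a single disease in Appendix 8, where an inclusive ratio would be trivially 1. This stands as far as it goes: the formula is not wrong in itself. It does not rescue the plan, because the no-comorbidity row and "cumulative proportion of population accounted for at each step will be calculated" need the exclusive meaning, and one undefined term has to serve both.

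A reader might infer that the clusters will be mis-ranked. The documents do not support that: Section 6.5 ranks by prevalence, so rank and cumulative share are untouched. The ratio is one of four inputs to a consensus decision and has no cut-off, so no cluster is mechanically included or excluded.

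It might also be said that the no-comorbidity row would receive an expected prevalence of 1 from an empty product. Nothing commits the plan to reporting a ratio there, and Appendix 8 already uses a dash where none is given.

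Finally, most of the magnitude is assumed. That is fair. The direction does not depend on the assumed prevalences, but the size does. That clusters with allergic rhinitis fare best depends on its being the commonest condition, which Section 1.0 offers only as a possibility.

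**Conclusion.** The point holds as a mismatch between the stated formula and the stated table, with the cluster definition left open. It goes beyond missing detail, because applying the Section 6.4 formula to the Section 6.5 table gives ratios whose value under independence is below 1 and varies by cluster. The size is at most 0.75 for any cluster without allergic rhinitis at 25% prevalence, and about 0.45 to 0.72 for the three example pairs. Across the assumed sets, the value under independence differs between pairs by a factor of 1.3 to 3.9. That is enough to reverse the order of two clusters on this criterion.

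These figures rest on reading the table as exact combinations, which its structure requires, and on assumed prevalences for eight of the nine diseases. On an inclusive reading the ratio is unbiased but the table does not work. The consequence is limited to a distorted selection criterion and does not extend to the prevalence results. It should be settled before the Phase 2 clusters are chosen.

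**What to change.** In Sections 6.4 and 6.5, define a cluster as an exact combination for the prevalence ranking and the cumulative percentage, and compute the observed/expected ratio with matched terms, by one of:

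- the exact count as observed, with expected = Π p over the diseases present × Π (1 − p) over the diseases absent; or
- the count of patients with at least the listed diseases as observed, with the plain product as expected.

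State which is used. Both equal 1 under independence, but the first reflects the whole nine-disease pattern and the second only the listed diseases. Use the inclusive definition for the overlap objective in Section 2.2 and the disease-pair graph in Section 6.6, and say so there.

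The cost is a sentence in the protocol and a line of code. No further data are needed, since either ratio comes from the same Phase 1 records.

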6.5 Identification and selection of comorbidity clusters (phase 1)

There are over 500 possible combinations of the 9 comorbidities of interest. The prevalence of each combination of comorbidities will be tabulated (including patients with no comorbidities) (see mock table in appendix 8). Clusters will be ranked by prevalence. The ratio of observed cases to expected for each cluster and cumulative proportion of population accounted for at each step will be calculated.

Visualisations of the frequency and age distribution of comorbidity in the asthma population will be produced. A table with the source data will accompany each figure. The first figure will chart the frequency of comorbidities in the study population (see illustrative example in appendix 9). The second figure will chart the mean number of comorbidities in the asthma population by age group and gender (appendix 10).

A small set of key comorbidity clusters will then be selected by consensus for further analysis in phase 2. This will be based on their clinical importance, prevalence, observed/expected ratio and cumulative proportion of population included.

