4.2 Inclusion and exclusion criteria

Inclusion criteria

Registered at a participating practice for at least one year prior to their index date and within the study period. In phase 1, the cross-sectional assessment of co-morbidity co-occurrence, the index date for each patient will be the earlier of the following dates: the last data collection from each practice and 6 months before patient deregistration (to avoid gaps in the clinical data due to late recording of patient deregistrations). For CPRD practices with linked HES data, the index date will be the earliest of the following dates: the last data collection from each practice, 6 months before patient deregistration, date of last HES record. In phase 2, the index date will be one year before the last data collection from each practice and 6 months before patient deregistration, to allow for one year of follow-up.

Patient had active asthma at their index date:

- a diagnosis of asthma at any time before their index date (using QOF Read codes: see Appendix 1); AND
- two or more prescriptions for an asthma medication in the preceding year.

Exclusion criteria

Any other chronic lower respiratory condition recorded at any time (Read coded: see Appendix 2). These are:

- Lung disease due to external agents, other than smoking, such as occupational agents.
- Active COPD (a Read code at any time + medication in the last year of follow-up).
- Bronchiolitis obliterans.
- Pulmonary fibrosis.
- Pulmonary hypertension.
- Cystic fibrosis

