5.2 Identifying comorbidities of interest

The nine T2-type comorbidities of interest (atopic dermatitis; allergic rhinitis; chronic rhinosinusitis; nasal polyps; urticaria; allergic conjunctivitis; food allergy; eosinophilic oesophagitis; and anaphylaxis) will be identified by the presence of a Read code for the condition in the patient record. Anaphylaxis will also be identified by the prescription of adrenaline. Appendix 3 lists conditions where there are existing Read code definitions and those which will be developed during the study.

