13.4 Appendix 4: GINA step definition

GINA Step:	Drug Class Groups:
1	SABA or LABA +/- SABA(although discouraged without ICS)
2	Low dose (LD) ICS ¹ +/- SABA or LTRA +/- SABA or THEO +/- SABA or LABA + THEO +/- SABA(although discouraged without ICS) or
3	LD ICS + LABA +/- SABA (adults) / Medium dose (MD) ICS + LABA +/- SABA (children) or MD ICS +/- SABA LD ICS + LTRA +/- SABA or LD ICS + THEO +/- SABA or LD ICS + LABA + LTRA +/- SABA or LD ICS + LABA + THEO +/- SABA or LD ICS + LABA + LTRA + THEO +/- SABA or
4	MD /High dose (HD) ICS + LABA +/- SABA (adults) or HD ICS + LABA +/- SABA (children)
5	MD/HD ICS + LTRA +/- SABA or MD/HD ICS + THEO +/- SABA or MD/HD ICS + omalizumab or ICS + LABA + Maintenance oral steroids +/- SABA or ICS + LTRA + Maintenance oral steroids +/- SABA or ICS + THEO + Maintenance oral steroids +/- SABA or Maintenance oral steroids

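### The Phase 1 observed/expected ratio pools all ages, so part of it reflects shared or opposed age patterns and not association between the diseases

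*Protocol*

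**What the plan says.** **Population.** Protocol Section 4.2 requires that a patient be "Registered at a participating practice for at least one year prior to their index date and within the study period" and have active asthma. Neither the inclusion nor the exclusion criteria mention age. Appendix 4 assigns GINA step by different rules for adults and children ("adults) or HD ICS + LABA +/- SABA (children"), so both are expected in the data.

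**Case definition.** Under Section 5.2 a comorbidity "will be identified by the presence of a Read code for the condition in the patient record". No time window is attached.

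**The ratio.** Section 6.4 obtains cluster prevalence by "dividing the number of patients in the cluster by the total number of patients eligible for inclusion in the study". The expected prevalence is "the product of the prevalence of each individual disease in the cluster". Neither has an age term, and the Appendix 8 mock table is not split by age.

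**Its use.** Section 6.5 has clusters ranked by prevalence and then a small set chosen by consensus: "This will be based on their clinical importance, prevalence, observed/expected ratio and cumulative proportion of population included".

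**Where age appears.** Section 6.5 promises visualisations of the age distribution of comorbidity, with source tables. The one specified (Appendix 10) is the average comorbidity count by age and gender. Section 6.6 describes each cluster by age, but only in Phase 2, for clusters already chosen. The confounder adjustment in Section 6.8 applies to the multivariable models, and the record-length sensitivity analysis in Section 6.9 repeats Phase 2 only.

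**The concern.** A product of marginal prevalences is the right expectation under independence only if the diseases are independent in the pooled population. Two diseases that are unrelated at every age but both commoner in children will still coincide more often than that product predicts, because children supply most of the cases of each. Two diseases with opposed age patterns will coincide less often. The pooled ratio cannot tell this apart from association within age.

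The ratio is one of the four inputs to the choice of clusters, and Phase 2, including the resource-use and cost work, is confined to the clusters chosen. Describing the clusters by age afterwards cannot bring back a combination that was passed over. Nor does sample size help: with about 220,000 patients in Phase 1 (Section 6.1), an age-driven ratio can look precise.

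**Working it through.** **The plan's own figures.** Nine conditions give 2^9 = 512 combinations including none, which agrees with "There are over 500 possible combinations of the 9 comorbidities of interest". The Appendix 8 mock rows are coherent: 2000/0.200 = 350/0.035 = 50/0.005 = 10,000.

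**Formula.** Let w_k be the share of age group k and p_ik the prevalence of disease i in that group, with diseases independent within each group. Counting patients with at least the named diseases:

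- Observed = Σ_k w_k Π_i p_ik
- Expected as in Section 6.4 = Π_i (Σ_k w_k p_ik)
- For a pair, observed/expected = 1 + Cov_age(p_A, p_B) / (mean p_A × mean p_B), where the covariance is taken across age groups.

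The direction follows from the sign of the covariance: above 1 for a shared age pattern, below 1 for opposed ones.

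**Inputs.** The documents give no age mix and no age-specific prevalence. Assumed here: two groups (children, adults), a child share of 10–40%, and a prevalence ratio r of 1.5–5 between the groups. The lower prevalence is set at 4%; its level cancels from the ratio.

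**One case in full: 20% children, r = 3 (12% against 4%).**

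- Mean prevalence of a childhood-pattern disease: 0.2×0.12 + 0.8×0.04 = 0.056. Adult-pattern disease: 0.2×0.04 + 0.8×0.12 = 0.104.
- Childhood pair: (0.2×0.12² + 0.8×0.04²)/0.056² = 0.00416/0.003136 = 1.33.
- Adult pair: (0.2×0.04² + 0.8×0.12²)/0.104² = 0.01184/0.010816 = 1.09.
- Opposed pair: 0.12×0.04/(0.056×0.104) = 0.0048/0.005824 = 0.82.
- Childhood triad: (0.2×0.12³ + 0.8×0.04³)/0.056³ = 0.0003968/0.0001756 = 2.26.

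**Range.** Every entry would be 1.00 if the ratio measured only association within age.

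| Assumption | Childhood pair | Adult pair | Opposed pair | Childhood triad |
|---|---|---|---|---|
| 20% children, r = 1.5 | 1.03 | 1.02 | 0.97 | 1.11 |
| 20% children, r = 2 | 1.11 | 1.05 | 0.93 | 1.39 |
| 20% children, r = 3 | 1.33 | 1.09 | 0.82 | 2.26 |
| 20% children, r = 5 | 1.79 | 1.15 | 0.66 | 4.42 |
| 10–40% children, r = 1.5–5 | 1.02–1.80 | 1.01–1.33 | 0.57–0.99 | 1.07–4.88 |

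**Exact combinations.** The cumulative percentage in Appendix 8 reaches 100%, so its rows are exact combinations, while the expected value multiplies only the diseases present. The no-association value is then not 1.0. I took an assumed nine-disease example with 20% children and these child/adult prevalences: eczema 45/20%, rhinitis 20/30%, rhinosinusitis 1/8%, polyps 0.2/4%, urticaria 10/10%, conjunctivitis 12/12%, food allergy 8/1.5%, oesophagitis 0.1/0.1%, anaphylaxis 5/1.5%. Independence within age is assumed throughout.

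| Combination | Ratio with no age effect | Ratio with age effect only |
|---|---|---|
| Eczema + food allergy | 0.50 | 0.78 |
| Rhinosinusitis + polyps | 0.41 | 0.52 |
| Food allergy + polyps | 0.39 | 0.22 |
| Urticaria + conjunctivitis (flat in age) | 0.46 | 0.46 |

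The age shift is in the same direction as before, but relative to a reference value that is itself below 1.

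**With the expectation formed within age.** Replacing the expected value by Σ_k w_k Π_i p_ik makes the at-least-these ratio 1.00 for every set of diseases independent within the bands used.

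**The case against.** The strongest reply is that Phase 1 is descriptive. Its objective in Section 2.2 is to estimate how often each combination occurs and to select common ones. Ranking is by prevalence, and prevalence and cumulative proportion are valid all-age figures that this point does not touch. The ratio has no cutoff and no stated weight, and it is used alongside clinical judgement. This stands, and it limits the consequence.

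The size is also open. With a 1.5-fold gradient the distortion of a pair is a few hundredths. Because a code counts whenever it was recorded, and Section 6.9 assumes that relevant history follows the patient, adults may keep childhood codes, which would narrow the gradients. That stands too.

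Three stronger readings are tempting, and the documents do not support them.

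- A reader might infer that an age-driven triad would pass the ratio of 2 in the Appendix 11 caption. That caption belongs to another study's figure, reproduced as a mock, and it also requires a prevalence of at least 1%. In the nine-disease example, eczema + food allergy + anaphylaxis has an at-least-these ratio of 2.57 but a prevalence of 0.2×0.45×0.08×0.05 + 0.8×0.20×0.015×0.015 = 0.000396, or 0.04%. The protocol itself sets no threshold.
- A reader might infer that the ratio favours childhood combinations only. Adult-pattern pairs are raised as well.
- A reader might infer that any value above 1 marks an artefact. For the exact combinations of Appendix 8 the reference is not 1.0, so the shift must be judged against the correct no-association value.

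It can also be said that age-stratified tables are often left to the SAP. But the protocol does fix the formula and its use in selection, and the formula has no age term.

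**Conclusion.** The point holds as a weakness of the stated ratio, not as a demonstrated error in the clusters. From the text alone: there is no age limit, the expectation is an all-age product, and the ratio is a named selection criterion. From algebra: a shared age pattern raises the ratio and an opposed one lowers it, relative to the correct no-association value.

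The size rests entirely on assumed age mixes and gradients. It is negligible for pairs at 1.5-fold, moderate for pairs at 3-fold, and large for triads from about 3-fold upwards. Whether the selected set would change cannot be determined from the protocol. It is worth correcting because the choice is made once, before Phase 2, and the correction is cheap.

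**What to change.** In Sections 6.4 and 6.5, keep the all-age population and the pooled table, and add the following.

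1. Compute the expected count of each combination within a few broad age bands and sum over bands. Report this age-standardised ratio beside the pooled one, and use it as the ratio criterion.
2. Print the Appendix 8 table for children and for adults separately, before the consensus step.

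Observed and expected should count the same thing, either at-least-these or exact combinations. Age banding does not settle that on its own, and 1.0 is the reference only when they match.

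The cost is a little more analysis and two further tables in Phase 1. Rare combinations will have sparse counts in some bands, which is why the bands should be few and broad. Association with age inside a band remains, but is reduced. The prevalence ranking and the cumulative proportions do not change.
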